4.9 STUDY PROCEDURES

Subjects will return to the study center at 1 month (30 days \pm 7 days), 6 months (180 days \pm 30 days), 12 months (360 days \pm 30 days), 24 months (720 days \pm 60 days), and 36 months (1080 days \pm 60 days) following the procedure for a follow-up evaluation. The subject will undergo lower-extremity arterial and venous duplex ultrasounds, venous health questionnaires, QOL surveys, walk test, and examined for any post-procedural complications or adverse events.

4.9.1 Initial Eligibility

After subjects have signed an informed consent form and before the scheduled interventional procedure, subjects will undergo an

initial eligibility evaluation by the investigator. Medical history within the previous 30 days and imaging performed within the previous 180 days may be used for this initial eligibility evaluation. The evaluation may consist of the following:

- Pre-procedural imaging (CT, MRA, Angio, etc.)
- Pre-procedural venous ultrasound
- Review of inclusion/exclusion criteria

Subject eligibility and pre-procedure imaging studies will be reviewed to assess subject eligibility. This process may be done in collaboration with a screening committee, clinical site investigators, core lab assessment, medical advisory committee, etc. in an effort to assist the sites in eligibility requirements.

4.9.2 Baseline Evaluation

Subjects will undergo a baseline evaluation. This evaluation may be conducted from an office visit within the previous 30 days. The evaluation will consist of the following:

- Subject's demographic data (sex and date of birth)
- Medical and surgical history review, including peripheral vascular history
- Rutherford clinical category
- Venous Clinical Severity Score
- Villalta Scale
- Routine Laboratory Tests (CBC and Chem-7; urine pregnancy test, if applicable)
- eGFR
- Ankle Brachial Index or Toe-Brachial Index
- EQ-5D-5L QOL survey
- VascuQOL survey
- SF-12
- 6-Minute Walk Test (subgroup of subjects only)
- Review of inclusion/exclusion criteria

Note: The 6-Minute Walk Test is not routinely performed at all clinical sites; therefore, select sites shall complete a 6MWT on select subjects as agreed upon. This will therefore result in a subgroup of clinical sites and subjects and not be studywide.

4.9.3 Vascular Access and Guidewire Delivery

Investigators will access the target lesion and the corresponding ipsilateral vein using standard percutaneous techniques and devices. Patient eligibility will be confirmed prior to insertion of the study device, based on procedural imaging and sheath placement.

After eligibility confirmation, the PQ Crossing Device and the PQ Snare will be used to deliver a guidewire from the arterial segment proximal to the target lesion, through the femoral vein and back into the reconstituted artery distal to the target lesion. The number of deployment attempts for guidewire placement access at each anastomosis will be recorded.

4.9.4 TORUS Stent Graft Placement

TORUS Stent Grafts of appropriate dimension are selected by investigators visual estimates of arterial diameter. SGs are then deployed in series, starting distally, until the bypass is complete. After placement, the Investigator uses a standard balloon dilatation catheter to complete stent apposition, ensuring that the balloon is only inflated within the TORUS Stent Graft's lumen.

4.9.5 Anticoagulation and Dual Antiplatelet Therapy

Effective anticoagulation therapy should be maintained throughout the procedure with heparin (per hospital or institutional standards, recommending a minimum of ACT >250) or a clinically acceptable alternative of the treating physician's choice. Subjects must be treated with antiplatelet and/or anticoagulation for a minimum of three years. **Table 5** shows the recommendation for administration of these medications, but the final decision is up to the operator and may include other antiplatelet or anticoagulation agents not identified.

Table 5: Administration of Anticoagulations and Dual Antiplatelet Medications

Medication	Peri-Procedure	Intra-Procedure	Post-Procedure
	(\pm 24 hours of Index Procedure)		

Aspirin	Minimum loading dose of 75 mg required, if not on long-term aspirin therapy	N/A	A minimum of 75 mg per day indefinitely
Clopidogrel* (or similar antiplatelet agent or alternative agent per investigator discretion)	Minimum loading dose of 300-600 mg required, if not on long-term clopidogrel therapy	N/A	Clopidogrel 75 mg per day for a minimum of 3 years (or per prescribing dose if other similar antiplatelet agent or alternative agent per investigator discretion)
Heparin / Bivalirudin	N/A	Maintain anticoagulation per hospital / institution standard of care (minimum of ACT >250 sec recommended)	N/A

* For patients requiring anticoagulation therapy (NOAC or OAC), antiplatelet monotherapy with either aspirin or clopidogrel for 3 years, followed by aspirin therapy or other anti-coagulant indefinitely is recommended, using investigator discretion for the best interest and safety of the subject.

4.9.6 Procedural Evaluation

Final eligibility will be determined based on imaging study and sheath placement. Information on the lesion being treated and the specific vasculature used in its treatment will be collected. The procedural evaluation will consist of the following:

- Lesion characteristics (lesion length and TASC II classification)
- Procedure start and finish times
- Access sites used
- Number of attempts to create each anastomosis
- Complications or adverse events
- Review of angiographic inclusion/exclusion criteria

4.9.7 Discharge Evaluation

The discharge evaluation will consist of:

- Physical examination and health status
- Complications or adverse events
- Anticoagulations and Dual Antiplatelet Medications

4.9.8 Follow-Up Evaluations

Subjects will return to the study center for follow-up evaluations at 1 month (30 days \pm 7 days), 6 months (180 days \pm 30 days), 12 months (360 days \pm 30 days), 24 months (720 days \pm 60 days), and 36 months (1080 days \pm 60 days) post-index procedure. Follow-up evaluations will include:

- Physical examination and health status
- Rutherford score
- Ankle-Brachial Index/Toe-Brachial Index
- Venous Clinical Severity Score
- Villalta Scale
- Arterial and Venous duplex-ultrasound assessment
- EQ-5D-5L QOL Survey (Baseline, 1 and 12 months)
- VascuQOL Survey (Baseline, 1 and 12 months)
- SF-12 (Baseline, 1 and 12 months)
- 6-minute Walk Test (Baseline, 1 and 12 months, sub-group of subjects only)
- Stent Graft X-ray (12 months)
- Complications and adverse events
- Anticoagulations and Dual Antiplatelet Medications

4.9.9 Subject Lost to Follow-Up

A subject will be considered lost to follow-up and terminated from the study when all of the following criteria have been met:

- On the final study visit with supporting documentation of three unsuccessful attempts on three different days over a period of three (3) months at both study visits by the Investigator or his/her designee to contact the subject or next of kin, one of which should be by certified mail with signature confirmation.
- Prior agreement of the Sponsor to remove the subject from the clinical investigation.

5.0 ASSESSMENT OF EFFICACY

5.1 PRIMARY EFFECTIVENESS ENDPOINT

The primary effectiveness endpoint is defined as primary patency at 12 months as evidenced by a peak systolic velocity ratio (PSVR) ≤ 2.5 from DUS and no clinically-driven re-intervention within the stented segment.

The primary effectiveness endpoint hypotheses are:

- H0: 12-month success rate of the PQ Bypass System $\leq 60.4.0\%$
- HA: 12-month success rate of the PQ Bypass System $> 60.4.0\%$

Based on a PG of 60.4%, a sample size of 202 with 181 subjects with evaluable data at 12 months would provide 91% power to test the primary effective hypothesis at the one-sided alpha level of 0.025, if the PQ Bypass Stent Graft success rate is at least 72%. The Exact Test Method and commercial software PASS14 was used to determine the sample size.

In order to ensure sufficient subjects are available at 12 months for assessment of the primary effectiveness endpoint (i.e., to account for missing data), an additional 21 subjects (approximately 10% estimated attrition rate) may be enrolled, making the total study sample size equal to 202 subjects.

To meet the primary effectiveness endpoint of the IDE Study with a sample size of 202 enrolled and 191 evaluable subjects with 12 month primary patency data, at least 124 subjects ($\geq 68.1\%$) must experience 12-month primary patency (calculated using the exact confidence interval).

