7.1.1. Primary Effectiveness

The primary effectiveness endpoint is defined as primary patency at 12 months as evidenced by a peak systolic velocity ratio (PSVR) ≤ 2.5 from DUS and no clinically-driven re-intervention within the stented segment.

The primary effectiveness endpoint hypotheses are:

- H0: 12-month success rate of the PQ Bypass System $\leq 60.4\%$
- HA: 12-month success rate of the PQ Bypass System $> 60.4\%$

Based on a PG of 60.4%, a sample size of 202 with 181 subjects having evaluable data at 12 months would provide 91% power to test the primary effective hypothesis at the one-sided alpha level of 0.025, if the “true” PQ Bypass Stent Graft success rate is at least 72%. The Exact Test Method and commercial software PASS14 was used to determine the sample size.

In order to ensure sufficient subjects are available at 12 months for assessment of the primary effectiveness endpoint (i.e., to account for missing data), an additional 21 subjects (approximately 10% estimated attrition rate) may be enrolled, making the total study sample size equal to 202 TASC II D and complex TASC C subjects.

To meet the primary effectiveness endpoint of the IDE Study with a sample size of 202 enrolled and 181 evaluable subjects with 12 month primary patency data, at least 124 subjects ($\geq 68.1\%$) must experience 12-month primary patency (calculated using the exact confidence interval).

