7.1.2. Primary Safety

The primary safety endpoint of the PQ Bypass Detour II IDE Study is the freedom from MAE rate at 30 days following stent graft implantation, and includes:

- Death
- Target lesion revascularization (TLR)
- Amputation of the index limb
- Symptomatic deep vein thrombosis (DVT)
- Pulmonary embolism (PE)
- Procedure related bleeding requiring any transfusion of packed red blood cells or surgery

The primary safety endpoint hypotheses are:

- H0: 30-day Freedom from MAE rate of the PQ Bypass System $\leq 84\%$
- HA: 30-day Freedom from MAE rate of the PQ Bypass System $> 84\%$

The rate of freedom from 30-day MAE for the PQ Bypass System is expected to be no less than 92%. Based on a PG of 84% and an estimated 30-day freedom from MAE rate of 92% for the PQ Bypass System, a sample size of 169 evaluable subjects provides 88% power to test the primary safety hypothesis at the one-sided alpha level of 0.025. The Exact Test Method and Commercial software PASS14 was used to determine the sample size. The final sample size is based on the number required to test the primary effectiveness hypothesis (N=181 including attrition). The primary analysis population will include 202 TASC II D and complex TASC C subjects.

To meet the primary safety endpoint of the IDE Study with a sample size of 181 evaluable subjects (the actual number of subjects who are free from MAEs at 30 days MAE can be no less than 163 subjects ($\geq 89.6\%$)).

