7.3.1. Missing Data

Subjects free from clinically-driven target lesion revascularization within the stented segment but do not have sufficient follow-up to assess the primary effectiveness endpoint will be treated as having missing data for the primary effectiveness endpoint. To further evaluate the impact of missing data on the primary

effectiveness endpoint, Kaplan-Meier methods, will also be used to estimate the 12-month primary patency rate.

For the primary safety endpoint analysis, the denominator for each parameter in the safety measures will be the number of subjects who had sufficient follow up (at least 23 days for 30-day visit) plus any subjects who had an event prior to the milestone visit.

All subjects will be accounted for in the study report, including the reasons for any subjects exiting the study early.

Every effort will be made to collect all data points contributing to the primary effectiveness endpoint in the study. The sponsor attempts to minimize the amount of missing data by appropriate management of the prospective clinical trial, proper screening of study subjects, and training of participating investigators, monitors and study coordinators. In order to further assess the potential impact of missing data on the primary effectiveness endpoint analyses, the following sensitivity analyses will be performed:

- Worst-Case Scenario: Each missing value for the primary effectiveness endpoint will be treated as a failure. If this still results in rejection of the null hypothesis then no further missing data imputation analyses will be performed for the endpoint.
- If the conclusion is not upheld with the worst-case scenario approach, then the multiple imputation method will be used. A logistic regression model will be used and fifteen imputed datasets will be generated.
- Additionally a tipping point analysis will be performed. The proportion of missing values assigned the status of 'failure' will be sequentially increased to identify the point at which the study conclusions change (i.e., the null hypothesis is no longer rejected).

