7.4 EFFICACY ANALYSES

7.4.1. Primary Effectiveness Analysis

The MITT cohort will be used to evaluate the primary effectiveness endpoint. All subjects in the MITT population that have a clinically-driven re-intervention within the stented segment that occurs within 360 days of the index procedure will be considered a failure for the primary effectiveness endpoint. All subjects free from clinically-driven re-intervention within the

stented segment who meet the definition of stent graft patency with at least 11 months (330 days) of follow-up will be considered successful with respect to the primary effectiveness endpoint. Subjects free from clinically-driven re-intervention within the stented segment but do not have sufficient follow-up to assess the primary effectiveness endpoint will be treated as missing data.

The primary effectiveness hypothesis will be tested by calculating the one-sided 97.5% confidence limit, using the Exact method. If the lower limit exceeds the performance goal of 60.4% the primary effectiveness hypothesis will be met.

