7.5 SAFETY ANALYSES

7.5.1. Primary Safety Endpoint Analysis

The primary safety endpoint is evaluated on a per subject basis and will be calculated as the percent of all ITT subjects with sufficient follow-up that are free from all elements of the primary safety endpoint composite at 30 days. The primary safety hypothesis will be tested by calculating the lower one-sided 97.5% confidence limit, using the Exact method, for the rate of freedom from MAEs. If the lower limit exceeds the performance goal of 84%, the primary safety hypothesis will be met.

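### The printed pass counts for both primary endpoints do not match the exact lower-limit test: 124 of 191 fails the 60.4% goal, and 124 of 181 and 163 of 181 are each one subject too strict

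*Combined protocol and SAP*

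**What the plan says.** Section 5.1 gives two evaluable numbers for the same endpoint. Its power statement reads "a sample size of 202 with 181 subjects with evaluable data at 12 months would provide 91% power", for a goal of 60.4%, a true rate of 72% and a one-sided alpha of 0.025. Its pass mark reads "sample size of 202 enrolled and 191 evaluable subjects with 12 month primary patency data, at least 124 subjects", printed as 68.1% and attributed to the exact confidence interval. Section 7.1.1 repeats the pass mark with a different N: "sample size of 202 enrolled and 181 evaluable subjects with 12 month primary patency data, at least 124 subjects", again 68.1%.

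For safety, Section 7.1.2 takes 181 evaluable subjects and says "the actual number of subjects who are free from MAEs at 30 days MAE can be no less than 163 subjects", printed as 89.6%. The same section says the final "sample size is based on the number required to test the primary effectiveness hypothesis (N=181 including attrition"). Sections 5.1 and 7.1.1 instead make 181 the evaluable number and reach 202 by adding 21 for attrition.

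The analysis sections define success by the exact one-sided 97.5% lower limit. Section 7.4.1: "If the lower limit exceeds the performance goal of 60.4% the primary effectiveness hypothesis will be met". Section 7.5.1: "If the lower limit exceeds the performance goal of 84%, the primary safety hypothesis will be met".

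**The concern.** A pass count is only the exact rule evaluated at one N, so count, percentage and N must agree with each other and with the rule. Here they do not. One count pairs with two different N, and neither printed percentage equals its count divided by its N.

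The study's success rests on these two tests. Sections 5.1 and 7.1.1 word the count as a requirement, Section 7.1.2 words it as a floor, and nothing says whether the count or the confidence limit prevails. A borderline result could be claimed as a success under one section and called a failure under another, and the choice would then be made after the data are known.

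**Working it through.** **Inputs.** Effectiveness: goal p0 = 0.604, assumed rate p1 = 0.72, N = 181 or 191 (5.1, 7.1.1). Safety: p0 = 0.84, p1 = 0.92, N = 169 for power and 181 for the count (7.1.2). One-sided alpha is 0.025 for both. Rule: exact lower limit above the goal (7.4.1, 7.5.1).

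**Formulas.** For x successes in n, the exact (Clopper-Pearson) lower limit L is the 0.025 quantile of Beta(x, n − x + 1). The pass count is the smallest x with L > p0. Type I error is P(X ≥ x | n, p0) and power is P(X ≥ x | n, p1), both binomial.

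**The plan's own figures first.** 181/(1 − 0.10) = 201.1, rounded up to 202, so the enrolment figure reproduces. Exact power for effectiveness at N = 181 (pass count 123) is 90.1%, against 91% printed. For safety at N = 169 (pass count 152) it is 86.9%, against 88% printed. Both agree to about one point. The pass counts do not reproduce:

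| Endpoint | x/N | Percent | Exact lower limit | Goal | Result |
|---|---|---|---|---|---|
| Effectiveness, as printed in 5.1 | 124/191 | 64.9 | 57.7% | 60.4% | fails |
| Effectiveness | 128/191 | 67.0 | 59.86% | 60.4% | fails |
| Effectiveness, minimum at 191 | 129/191 | 67.5 | 60.403% | 60.4% | passes |
| Effectiveness | 122/181 | 67.4 | 60.05% | 60.4% | fails |
| Effectiveness, minimum at 181 | 123/181 | 68.0 | 60.63% | 60.4% | passes |
| Effectiveness, as printed in 7.1.1 | 124/181 | 68.5 | 61.20% | 60.4% | passes, one above the minimum |
| Safety | 161/181 | 89.0 | 83.45% | 84% | fails |
| Safety, minimum at 181 | 162/181 | 89.5 | 84.09% | 84% | passes |
| Safety, as printed in 7.1.2 | 163/181 | 90.1 | 84.74% | 84% | passes, one above the minimum |

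**Other interval methods.** Wilson, Wald and continuity-corrected Wald limits give 122 or 123 for effectiveness and 161 or 162 for safety at N = 181. None gives 124 or 163.

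**Where the printed figures fit.** 124/182 = 68.1% and 163/182 = 89.6%, and both are the exact minima at N = 182 (lower limits 60.83% and 84.18%; one success fewer gives 60.26% and 83.54%). This suggests that counts computed for 182 were not updated. That is an inference, because 182 appears nowhere in the documents.

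**Effect if the printed counts were enforced.**
- 124 of 191: type I error 0.114 instead of at most 0.025.
- 124 of 181: power falls from 90.1% to 87.0%. The 3.1 points are P(X = 123 | 181, 0.72).
- 163 of 181: power falls from 91.1% to 86.4%. The 4.8 points are P(X = 162 | 181, 0.92).

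**The safety N need not be 181.** Section 7.3.1 says "the denominator for each parameter in the safety measures will be the number of subjects who had sufficient follow up" (at least 23 days), plus anyone with an earlier event. The 21-subject allowance is for missing 12-month data, so the 30-day N can lie anywhere up to 202. At 202 the minimum is 181 (89.6%, lower limit 84.5%); 180 gives 83.98% and fails.

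**The case against.** The strongest reply is that the decision rule is clear enough. Sections 7.4.1 and 7.5.1 say how each hypothesis is tested and when it is met. The counts are conditional on a stated N, and 5.1 and 7.1.1 describe theirs as derived from the exact interval, so they can be read as illustrations. The 191 looks like a one-digit slip, contradicted by the 181 earlier in the section, by 202 − 21 and by the matching sentence in 7.1.1. At 181 the error is one subject, in the conservative direction, and matters only on an exact hit. The power gaps are about one point and exact power is saw-toothed in N (90.9% at 180, 91.2% at 183). The safety count at 202 is not an error in the text, since 163 is tied to 181.

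Much of this stands. The tests as specified have correct type I error, 191 is probably a slip, the power differences change no design decision, and the 202 figure only illustrates how a fixed count dates. What does not go away is that three sections print wrong thresholds as requirements, that 7.1.2 does not even mention the exact interval beside its count, and that no precedence sentence exists. The fit at 182 explains how the error may have arisen, but 181 is the evaluable number the text supports.

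**Conclusion.** The point holds: the counts are wrong as written. At 191 the printed 124 is five below the exact minimum of 129 and fails the goal. At 181 both printed counts are one above the minimum, 124 against 123 and 163 against 162. Both percentages, and the description of 181 as including attrition, are also inconsistent with the stated numbers.

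The consequence is limited. If 7.4.1 and 7.5.1 are followed, the conclusion of the study is unaffected. The printed counts would matter only if someone applied them and, at N = 181, only on an exact hit. This rests on the Clopper-Pearson limit being the exact method meant, on 181 as the planned evaluable number, and, for the probabilities, on the plan's own true rates of 72% and 92%. It should be fixed, but it does not threaten the design.

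**What to change.** - Section 5.1: change 191 to 181.
- Sections 5.1 and 7.1.1: print the minimum as 123 of 181 (68.0%).
- Section 7.1.2: print the minimum as 162 of 181 (89.5%), and describe the sample size as 181 evaluable, 202 including attrition.
- All three sections: add a sentence that the exact one-sided 97.5% lower limit at the actual evaluable N (7.4.1, 7.5.1) decides, and that the count only illustrates it at the planned N.
- While these lines are open, restate exact power as 90% for effectiveness at 181, and for safety as 87% at 169 or 91% at 181. This is minor.

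The sponsor should confirm 181 as the planned evaluable number before editing, given the fit at 182. The cost is a text correction. The tests, performance goals and sample size stay as they are, and two printed power figures fall by about one point.

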6.0 ASSESSMENT OF SAFETY

6.1 PRIMARY SAFETY ENDPOINT

The primary safety endpoint of the PQ Bypass Detour II IDE Study Freedom from a major adverse event (MAE) at 30 days post-procedure defined as any occurrence of the following events: Death, Clinically-Driven Target Lesion Revascularization (CD-TLR), Amputation of the Treated Limb, Symptomatic Deep Vein Thrombosis (DVT), Pulmonary Embolism, or procedure-related bleeding requiring any transfusion of packed red blood cells or surgery.

